9.7.2.2 Analysis of secondary endpoints

Binary secondary endpoints:

The binary secondary endpoints include:

- Incident neoplasm
- Incident T2DM

Incidence rates will be calculated for both endpoints and compared to aggregated data of incident neoplasms from the combined NordiNET/ANSWER study⁶ and incident T2DM from the GeNeSIS study.⁹ From both studies, the incidence rates for isolated GHD will be used for comparison. The SIR with a 95% confidence interval will be used as an additional estimate for neoplasms and new-onset T2DM.

 Protocol
 Date:
 17 July 2024
 Novo Nordisk

 Study ID: NN8640-4787
 Version:
 3.0
 3.0

 UTN: U1111-1294-5941
 Status:
 Final

Page:

25 of 48

Count-data secondary endpoints:

The analyses of the following secondary endpoints (counted from the baseline (week 0) to the EOS^a) will be done in the same way as the analysis of the primary endpoint:

• Number of AEs

EU PAS No.: Pending

- Number of SAEs
- Number of serious ADRs
- Number of medication errors

Continuous secondary endpoints

For the following secondary endpoints (clinical parameters), the change will be estimated by length of follow up and treatment duration.

- Height velocity
- Change in height velocity SDS
- Change in height SDS
- Change in IGF-I SDS
- Change in bone age

Patients reaching near adult height will be evaluated at EOS only for those who are expected to reach near adult height during the study. Change in height SDS in subjects reaching near adult height will be calculated from baseline (week 0) to EOS.

Note: Near adult height can be defined as height velocity <2 cm/year over the last 9 months and chronological age >16 years (males) or >15 years (females) or bone age >16 years (males) and >15 years (females).

IGF-I SDS will be used to evaluate treatment adherence assuming an increase in IGF-I SDS represents a response to GH treatment.

To deal with patients switching medication in-study and on-treatment analyses will be performed as defined below. The analyses will be repeated separately for GH treatment naïve and non-naïve patients previously receiving other GH treatment as data allows.

In-study

The observation period represents the time frame during which patients are considered to be part of the study, regardless of their adherence to somapacitan treatment. The in-study period starts at the time of informed consent and ends at the date of whichever comes first:

- EOS visit (last visit within the study duration)
- Withdrawal of informed consent date
- Other (e.g. patient is deceased, or physician is no longer providing data to GloBE-Reg)

On-treatment

This observation period represents the period in which patients are treated with somapacitan. This observation period is a part of the in-study observation period. The on-treatment period starts at the date of treatment start and ends at the first date of any of the following:

• Date of treatment stop of somapacitan

^aEOS will differ from patient to patient.

 Protocol
 Date:
 17 July 2024
 Novo Nordisk

 Study ID: NN8640-4787
 Version:
 3.0

 UTN: U1111-1294-5941
 Status:
 Final

 EU PAS No.: Pending
 Page:
 26 of 48

- EOS visit (last visit within the study duration)
- Withdrawal of informed consent date
- Other (e.g. patient deceased or physician no longer providing data to GloBE-Reg)

The following subgroup analyses will be performed if data allows:

- Sex
- Age groups:
 - o Females: 0-3, 4-8, 9-14, 15-18, >18 years
 - o Males: 0-3, 4-9, 10-15, 16-18, >18 years
- GH treatment dose (GH naive or non-naïve):
 - $0.04 \leq mg/kg/week \leq 0.08$
 - \circ 0.08<mg/kg/week \leq 0.16
 - o 0.16<mg/kg/week≤0.24
 - \circ 0.24<mg/kg/week \leq 0.34
- By country/regions
- By Tanner stage 1 and >=2

Age groups are different for females and males due to the different timing in puberty and in growth velocity. 19

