4.7 Variables

For the primary and secondary endpoints, data on the following variables will be extracted from the GloBE-Reg registry.

The number of ADRs from baseline to the EOS will be recorded as primary endpoint. Safety endpoints such as number of AEs, SAEs, serious ADRs, medication errors, incident neoplasm, incident T2DM from baseline (week 0) to EOS will be recorded as secondary endpoints. Additionally, other clinical parameters will also be recorded as secondary endpoints. Safety data will be collected by GloBE-Reg for the registered paediatric patients with GHD.

Incidence rates for neoplasms will be compared to incidence rates published in the combined NordiNET/ANSWER studies. 6-8 Similarly, incidence rates for T2DM will be compared to published results from the GeNeSIS study. 9.10 From both studies, the incidence rates for isolated GHD will be used for the comparison.

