4.10 Data analysis

Data from at least 400 paediatric patients with GHD (inclusive of both naïve and non-naïve) will be analysed using safety analysis set (SAS). The number of ADRs from baseline to EOS will be analysed. EOS will differ from patient to patient. AEs, SAEs and serious ADRs during the study period will be summarised by Medical Dictionary for Regulatory Activities (MedDRA) system organ class (SOC) and preferred term (PT). This summary is displayed with number and proportion of patients with at least one event, number of events and event rate (events per 100 patient-years of exposure).

The combined data from NordiNet[®] IOS and ANSWER studies will be used as external comparator for the occurrence of ADRs including neoplasms⁶⁻⁸. Data from the GeNeSIS registry will be used as external comparator for the occurrence of T2DM. ^{9, 10} The aggregated data from isolated GHD from both publications will be used for the comparison.

The standardised incidence ratio (SIR) with a 95% confidence interval will be used as an additional estimate for neoplasms and new-onset T2DM.

A statistical analysis plan (SAP) will be written, including a detailed elaboration of the statistical analyses. The SAP will be finalised before database lock. Data from the registry will be analysed and reported.

17 July 2024 Novo Nordisk Date:

Protocol Study ID: NN8640-4787 Version: 3.0 CONFIDENTIAL UTN: U1111-1294-5941 Status: Final EU PAS No.: Pending Page: 12 of 48

5 Amendments and updates

Amendment or update no	Date	Section of study protocol	Amendment or update	Reason
1	28 February 2024	General update	Update	Following PRAC
		of the protocol		review
2	17 July 2024	General update	Update	Following PRAC
		of the protocol		review

Protocol Study ID: NN8640-4787 17 July 2024 | Novo Nordisk Date: Version: 3.0 CONFIDENTIAL Status:

Page:

Final

13 of 48

UTN: U1111-1294-5941 EU PAS No.: Pending

Milestones 6

Milestone	Planned date
Start of data collection	Q4 2024
End of data collection	Q4 2034
Study progress report	To follow PSUR timelines ^a
Interim report	Q4 2030 (6 years from start of data collection)
Final report of study results	Q4 2035

^aAnnual progress reports, submitted with PSUR (when applicable).

Protocol

Study ID: NN8640-4787 UTN: U1111-1294-5941 EU PAS No.: Pending

CONFIDENTIAL

Date: Version: Status: Page: 17 July 2024 | **Novo Nordisk**3.0
Final
14 of 48

7 Rationale and background

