9.2.2 Inclusion criteria

For an eligible patient, all inclusion criteria must be answered 'yes'.

- 1. Treated with commercially available somapacitan according to local practice at the discretion of the physician.
- 2. Primary confirmed diagnosis of GHD as per local practice.
- 3. Male or female below 18 years of age at the time of signing informed consent in the GloBE-Reg.

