9.2.3 Exclusion criterion

For an eligible patient, the following exclusion criterion must be answered 'no'.

1. Patients with active malignancy or in treatment for active pre-existing malignancy.

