9.3.3 Covariates

The following baseline characteristics will be available from the GloBE-Reg data and overlap with the baseline characteristics from NordiNET/ANSWER and GeNeSIS:

- Sex
- Country
- Age at initiation of GH treatment (any GH treatment)
- Duration of GH Treatment at study inclusion (GH naïve or non-naïve patients)
- Height
- Weight
- BMI
- IGF-I
- Bone age
- Medical history of neoplasms
- Medical history of T2DM
- Diabetes risk factors: obesity

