9.7 Data analysis

9.7.1 Definition of analysis sets

The safety analysis will be based on the SAS. The SAS will consist of all patients exposed to somapacitan during study period.

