9.7.2.1 Analysis of primary endpoint

The primary endpoint is the number of ADRs from baseline to EOS. EOS will differ from patient to patient.

ADRs during the study period will be summarised by MedDRA SOC and PT. This summary is displayed with number and proportion of patients with at least one event, number of events, and event rate (events per 100 patient-years of exposure).

The combined data from NordiNet® IOS and ANSWER will be used as an external comparator for the occurrence of ADRs. The aggregated data from isolated GHD patients from the NordiNET/ANSWER study will be used for comparison of both baseline characteristics and ADR incidence rates. No statistical comparison is planned due to limitations in the observational nature of the data collection.

The correlation between ADR incidence and duration of somapacitan treatment will be analysed with Spearman rank-order correlation.

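### Section 9.7.2.2 compares neoplasm incidence in a cohort not limited to isolated GHD, and open to children with a past tumour, with an isolated-GHD rate, and no stated outcome split uses the neoplasm history collected

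*Protocol*

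**What the plan says.** **Who is in the study cohort.** Inclusion criterion 2 in Protocol section 9.2.2 is "Primary confirmed diagnosis of GHD as per local practice". The only exclusion, in section 9.2.3, is "Patients with active malignancy or in treatment for active pre-existing malignancy". Section 9.7.1 then sets the analysis population: "The SAS will consist of all patients exposed to somapacitan during study period". Section 9.2.4 adds that the registry's own entry criteria also apply, and that the study's criteria were deliberately kept few so that the cohort reflects ordinary practice.

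**What the neoplasm rate is compared with.** Section 9.7.2.2 takes the neoplasm comparator from NordiNet/ANSWER: "From both studies, the incidence rates for isolated GHD will be used for comparison". The abstract says the same in section 4.7 ("From both studies, the incidence rates for isolated GHD will be used for the comparison") and in section 4.10 ("The aggregated data from isolated GHD from both publications will be used for the comparison").

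**What is done with tumour history.** Section 9.3.3 lists "Medical history of neoplasms" among the baseline characteristics, and section 9.9 counts medical history as a potential confounder. The outcome splits in section 9.7.2.2 are GH-naïve versus non-naïve, then sex, age, dose, country or region, and Tanner stage. Neither neoplasm history nor type of GHD appears among them. Under section 9.7.2.1 the isolated-GHD data "will be used for comparison of both baseline characteristics and ADR incidence rates", and section 9.9 promises a discussion of comparability in the final report.

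**The concern.** The comparator is restricted by type of GHD and the study cohort is not. A child whose tumour is in the past and no longer treated meets the study's stated criteria, and any event in that child counts in the numerator of the neoplasm rate. If such children carry a higher neoplasm rate than children with isolated GHD and are commoner on the somapacitan side, the rate rises through case mix alone.

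Neoplasm is a named focus of the primary objective (section 8.1), and section 7 says the external comparison is there to support clinical conclusions. Few events are to be expected, so one or two extra could change how the result reads. The baseline comparison and the promised discussion can reveal an imbalance, but neither gives a rate free of it. The statement in section 9.7.2.1 that no statistical comparison is planned concerns ADRs and does not cover the neoplasm comparison.

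**Working it through.** **The plan's own figures.** The protocol gives no neoplasm rate, no expected neoplasm count and no share of patients with a past tumour. Its one sample-size calculation (Table 9-4) concerns a 2% ADR incidence. It reproduces to within 0.01 (n = 400: 1.02 to 3.90, against 1.02 to 3.89 in the table) and has no bearing here.

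**Inputs.** From the protocol: 400 patients, 5-year recruitment from Q4 2024, last visit Q3 2034. Assumed: even entry and no loss to follow-up; a share *s* with a past tumour of 2%, 5% or 15%; a neoplasm rate ratio *RR* of 2, 5 or 10 for those patients against isolated GHD; a reference rate of 0.2 to 1 per 1,000 patient-years; no drug effect; and otherwise equal rates.

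**Step 1: expected events.** Patient-years = 400 × (9.75 − 2.5) = 2,900. Expected events E = 2,900 × 0.0002 to 2,900 × 0.001 = 0.58 to 2.9.

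**Step 2: inflation if the comparator contains no such patients.** Factor = 1 + s(RR − 1).

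| s | RR 2 | RR 5 | RR 10 |
|---|---|---|---|
| 2% | 1.02 | 1.08 | 1.18 |
| 5% | 1.05 | 1.20 | 1.45 |
| 15% | 1.15 | 1.60 | 2.35 |

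**Step 3: in events.** Excess = s(RR − 1)E:
- 2%, RR 2: 0.02E = 0.01 to 0.06
- 5%, RR 5: 0.20E = 0.12 to 0.58
- 15%, RR 10: 1.35E = 0.8 to 3.9

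The share of all events arising in patients with a history is sRR/(1 + s(RR − 1)): 0.04/1.02 = 4%, 0.25/1.20 = 21% and 1.5/2.35 = 64%.

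**Step 4: chance of a false signal.** A false signal here means an exact Poisson 95% lower limit for observed/expected above 1 with no drug effect. At E = 2.9 this needs 8 or more events. The probability is 1.0% for a like-for-like cohort, 1.1% (2%, RR 2), 2.6% (5%, RR 5) and 37% (15%, RR 10).

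**Step 5: if the comparator also contains such patients.** With share *c* in the isolated-GHD stratum, ratio = (1 + s(RR − 1))/(1 + c(RR − 1)).

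| c | 2%, RR 2 | 5%, RR 5 | 15%, RR 10 |
|---|---|---|---|
| 0 | 1.02 | 1.20 | 2.35 |
| 1% | 1.01 | 1.15 | 2.16 |
| 5% | 0.97 | 1.00 | 1.62 |

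**Step 6: the estimate restricted to patients without a history.** Patient-years left = 2,900 × (1 − s) = 2,842, 2,755 or 2,465. If events fall in proportion, the log-scale confidence interval widens by 1/√(1 − s) = 1.010, 1.026 or 1.085. If patients with a history supply more than their share of events, the factor is √[(1 + s(RR − 1))/(1 − s)]: √(1.02/0.98) = 1.02, √(1.20/0.95) = 1.12 and √(2.35/0.85) = 1.66 for the three cases. Against a comparator with share c, the restricted estimate is off by 1/(1 + c(RR − 1)): 0.99 to 0.92 at c = 1% and 0.95 to 0.69 at c = 5%, for RR 2 to 10.

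**The case against.** The strongest reply is that both sides of the mismatch depend on things the protocol does not show. The word 'Primary' in inclusion criterion 2 is ambiguous. The registry's entry criteria also apply (section 9.2.4) and may limit who gets in. The protocol does not define isolated GHD or say whether that stratum excludes tumour history, and Step 5 shows that 5% in the comparator removes or reverses the bias in two of three cases. Nor does it say whether a recurrence counts as incident; if not, the relevant rate ratio falls. All of this stands, and it means that neither the size nor the direction is established.

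A second reply is that using a collected covariate is SAP work. That is fair for the detail. But the protocol itself fixes the comparator, the analysis set and the list of splits, and following them as written sets unlike populations against each other. A SAP can add the missing result, but it would have to go beyond what section 9.7.2.2 lists.

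Third, the shift is lost in noise in most scenarios. With 2.9 expected, observing 3 gives an exact 95% interval for observed/expected of about 0.21 to 3.0. This holds at the low end and fails at the high end.

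Two stronger readings are tempting. A reader might infer that an excess could not be interpreted at all. The documents do not support that: with roughly 0.6 to 3 events expected, each can be read against the patient's history, and section 9.4 says neoplasm details will be in the study data. A reader might also infer that the SIR has the same flaw. Its reference population is not named, but that is ordinary SAP content and no fault of the protocol.

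**Conclusion.** The concern holds as a mismatch that the protocol writes in: a cohort not restricted to isolated GHD and open to past, inactive tumours is compared with isolated GHD, with no stated outcome split on the relevant history. The likely error, if there is one, is a false alarm rather than false reassurance. That needs two conditions: patients with a past tumour have a higher neoplasm rate, and they are commoner in the cohort than in the comparator stratum.

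The size is a range over assumptions: x1.02 at a 2% share and RR 2, x1.20 at 5% and RR 5, x2.35 at 15% and RR 10. No document figure says where in that range the study will fall. It would be wrong to conclude that the somapacitan rate will be inflated, only that the plan as written offers no result that would show whether it was. The point merits a change because neoplasm is a named focus of the primary objective and the remedy uses data already collected.

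**What to change.** In section 9.7.2.2, add a sentence: the external neoplasm rate comparison will be presented in patients without a history of neoplasm alongside the whole-cohort result, and events in patients with a history will be listed separately. Fixing this now avoids having to defend a post-hoc exclusion if an excess appears.

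The cost is one extra table and some precision in the restricted estimate. At assumed shares of 2% to 15%, the log-scale interval is about 1% to 8.5% wider from lost patient-years alone, and wider still if patients with a history supply a disproportionate share of events (Step 6). If the isolated-GHD stratum itself contains such patients, the restricted estimate errs towards reassurance, by as much as x0.69 at 5% and RR 10. The whole-cohort result must therefore stay beside it.

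The restriction is only a partial cure. Patients without a neoplasm history are still not all isolated GHD, and that remaining difference belongs in the comparability discussion that section 9.9 already promises.

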Somapacitan is a long-acting hGH derivative, with a single amino acid substitution in the backbone to which a non-covalent albumin binding moiety has been attached. Somapacitan is intended for once weekly subcutaneous administration with the aim of reducing injection frequency and treatment burden and potentially decreasing the barrier to initiating and/or maintaining replacement therapy in GHD. The mechanism of action of somapacitan is via IGF-I. Daily GH injections can be burdensome for paediatric patients and their caregivers, disrupting and interfering with daily life. This could lead to non-adherence to prescribed replacement therapy and suboptimal clinical outcomes. 3.4

As part of the European marketing authorisation for somapacitan for the treatment of paediatric patients with GHD, Novo Nordisk A/S received a requirement from the Committee for Medicinal Products for Human Use (CHMP) under the European Medicines Agency (EMA) to conduct a non-interventional, observational registry-based study to investigate long-term safety and clinical parameters of somapacitan treatment in paediatric patients with GHD in the setting of routine clinical practice.

As per the RMP, the primary aim of this non-interventional, observational registry-based study is to assess the long-term safety profile of somapacitan with special focus on the important potential risks (neoplasm, T2DM, and medication errors). This post authorisation safety study (PASS) will also provide additional long-term safety information (AEs, SAEs and serious ADRs) and will further substantiate the evaluation of potential risks in relation to treatment with somapacitan.

The secondary aim is to investigate the clinical parameters in patients treated with somapacitan with regards to changes in height velocity SDS, height SDS, IGF-I SDS, and bone age.

To draw clinically relevant conclusions on long-term safety of somapacitan, this study will compare safety data with historical data from literature (NordiNet® IOS, ANSWER⁶⁻⁸ studies and GeNeSIS⁹. 10 registry) of paediatric GHD patients treated with daily somatropin.

Brief description of these external comparators has been outlined below:

NordiNet® IOS (study GHLIQUID-3676) and ANSWER (study HGH-2149)

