This registry-based study will only investigate paediatric patients from the GloBE-Reg who have GHD and have been treated with somapacitan.

Additional information on each of the safety concerns to be addressed by this PASS is provided below.

Long term safety

Novo Nordisk A/S has included 'long-term safety' as missing information in the RMP for paediatric GHD.

The paediatric pivotal trial NN8640-4263, included in the submission package, included safety information from subjects with up to one year (52 weeks) of somapacitan exposure (i.e., short term/intermediate term). No safety data for patients with >1 year (52 weeks) of somapacitan exposure were included. Therefore, 'long term safety' is classified as missing information in the RMP and is included as the primary objective in this PASS.

Neoplasms

GH is anabolic and mitogenic, and IGF-I is antiapoptotic. Both hormones can cause proliferation of normal and malignant cells. In general, hGH treatment increases the blood IGF-I levels, but data do not generally support a carcinogenic effect of treatment with GH and there is no established relationship between high blood IGF-I levels and the risk of a malignancy. 12-14

T2DM

Treatment with GH may decrease insulin sensitivity, particularly at higher doses in susceptible patients. Consequently, hyperglycaemia may occur in subjects with inadequate insulin secretory capacity. As a result, previously undiagnosed impaired glucose tolerance and overt T2DM may be unmasked during GH treatment.

Impaired insulin sensitivity is a hallmark of T2DM. This effect of GH has been partly linked to the lipolytic effects of GH resulting in increased plasma levels of free fatty acids, plasma glucose and insulin levels in the hours following injections of hGH. 15, 16

 Protocol
 Date:
 17 July 2024
 Novo Nordisk

 Study ID: NN8640-4787
 Version:
 3.0
 3.0
 Status:
 Final
 Final
 Final
 Final
 Page:
 16 of 48
 17 July 2024
 Novo Nordisk
 Nordisk
 16 of 48
 17 July 2024
 Novo Nordisk
 16 of 48
 17 July 2024
 Novo Nordisk
 17 July 2024
 Novo Nordisk
 18 of 48
 18 of

Medication error

When there are both daily and weekly GH products on the market, there is a risk that the once weekly product might be mistakenly (by the patient/caregiver) administered daily, which could lead to incorrect dose administration rate and overdose.

When patients are used to take their injection daily, there is a risk that this will continue.

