9.2 Setting

9.2.1 Study population

The planned number of patients to be included is at least 400 (both naïve and non-naïve).

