9.3.2.2 Secondary endpoint(s)

Safety

Table 9-2 Safety parameters (secondary endpoints)

Endpoint title	Time frame	Unit
Adverse events (AEs)	From baseline (week 0) to EOS ^a (up to 10 years)	Count
Serious adverse events (SAEs)	From baseline (week 0) to EOS ^a (up to 10 years)	Count
Serious adverse drug reactions	From baseline (week 0) to EOS ^a (up to 10 years)	Count
Number of medication errors	From baseline (week 0) to EOS ^a (up to 10 years)	Count
Incident neoplasm	From baseline (week 0) to EOS ^a (up to 10 years)	Yes/no
Incident T2DM	From baseline (week 0) to EOS ^a (up to 10 years)	Yes/no

^aEOS will differ from patient to patient.

Abbreviations: EOS = end of study, T2DM = type 2 diabetes mellitus.

Clinical parameters

Table 9-3 Clinical parameters (secondary endpoints)

Endpoint title	Time frame	Unit
Height velocity	Yearly	Cm/year
Change in Height Velocity SDS	Yearly	-10 to +10
Change in Height SDS	Yearly	-10 to +10
Change in IGF-I SDS	Yearly ^a	-10 to +10

 Protocol
 Date:
 17 July 2024
 Novo Nordisk

 Study ID: NN8640-4787
 Version:
 3.0
 3.0

 UTN: U1111-1294-5941
 Status:
 Final

Page:

22 of 48

Endpoint title	Time frame	Unit
Change in bone age	Yearly	Years and months
Reaching near adult height ^b	EOS ^b	Yes/no
Change in height SDS in subjects reaching near adult height ^b	From baseline (week 0) to EOS ^c (up to 10 years)	-10 to +10

Note: Near adult height can be defined as: height velocity <2 cm/year over the last 9 months and chronological age >16 years (males) or >15 years (females) or bone age >16 years (males) and > 15 years (females).

EU PAS No.: Pending

Abbreviations: EOS = end of study, IGF-I = insulin-like growth factor 1, SDS = standard deviation score

AEs will be split into all AEs, SAEs and serious ADRs through the evaluation of seriousness and causality entered in GloBE-Reg by the contributing clinics. Seriousness will be categorized into death, life-threatening experience, in-patient or prolongation of existing hospitalization, persistent or significant disability/incapacity or congenital anomaly/birth defect, and important medical event. Causality assessment will be categorized into probable, possible, and unlikely.

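### A rise in IGF-I SDS cannot be read as adherence in children whose reference value was already taken on GH treatment

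*Protocol*

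**What the plan says.** Section 9.7.2.2 lists "Change in IGF-I SDS" among the continuous secondary endpoints, as does Table 9-3, and then gives the marker a second use: "IGF-I SDS will be used to evaluate treatment adherence assuming an increase in IGF-I SDS represents a response to GH treatment". The sentence names the marker, the direction that counts (upward) and what that direction means. It exempts no group of patients.

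The nearest related provision follows shortly after: "The analyses will be repeated separately for GH treatment naïve and non-naïve patients previously receiving other GH treatment as data allows".

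Four other places bear on whether the assumption can hold:

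- Sections 9.2.1 and 9.5 plan at least 400 patients, naïve and non-naïve together, with no stated split or cap.
- Section 9.2.2 sets as its first inclusion criterion: "Treated with commercially available somapacitan according to local practice at the discretion of the physician". The other criteria concern the GHD diagnosis, age and active malignancy. None asks for a washout or an untreated IGF-I value.
- Section 7 (Neoplasms) states: "In general, hGH treatment increases the blood IGF-I levels". The same section says of the study drug: "The mechanism of action of somapacitan is via IGF-I".
- Section 7 (Medication error) expects children who move over from daily products: "When patients are used to take their injection daily, there is a risk that this will continue".

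**The concern.** Reading adherence from a rise presupposes a starting point from which taking the drug would produce a rise. A GH-naïve child measured before the first dose has such a starting point. A child moved from adequately dosed daily GH may not: the reference value already reflects GH treatment, and taking every weekly dose may simply hold it there. The same applies to a naïve child who was already on somapacitan when consent was signed, if the reference value is taken at consent.

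In these children, absence of a rise is compatible with full adherence. A report that follows the stated assumption would make switchers look less adherent than naïve children for a reason unrelated to how they take the drug. The SAP may add operational detail, but the protocol has already fixed the direction and its meaning, so a SAP that follows it inherits the problem.

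**Working it through.** The protocol gives no adherence figure and no mean or SD for IGF-I change, so there is no figure to reproduce. The check has two parts.

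**1. Does the assumption follow from the protocol's own text?**

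- Non-naïve patients are those who received another GH product before (Section 9.7.2.2).
- GH treatment raises blood IGF-I (Section 7), and somapacitan acts through the same marker.
- No washout or untreated IGF-I value is required (Sections 9.2.2 and 9.2.3).
- The in-study period starts at consent (Section 9.7.2.2). The decision to treat precedes the decision to include (Section 9.1.2), so a patient may already be on somapacitan at that point.

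Together these allow the reference value to be an on-treatment value. An increase is then not a necessary consequence of adherence.

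Nothing elsewhere fills the gap. Section 9.3.1 lists the treatment start date, initial dose and dose changes, and no other adherence measure is named. Section 9.9 discusses missing IGF-I values but not this limitation.

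**2. How often would an adherent patient show no increase?**

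This is an illustration only. Every input is an assumption, because the protocol supplies none. With a normally distributed change of mean m and standard deviation s in adherent patients:

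P(no increase | adherent) = Φ(−m / s)

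| Adherent group (assumed) | m | s = 0.7 | s = 1.0 | s = 1.3 |
|---|---|---|---|---|
| Switchers | 0 | 50% | 50% | 50% |
| Switchers | 0.25 | 36.0% | 40.1% | 42.4% |
| Switchers | 0.5 | 23.8% | 30.9% | 35.0% |
| Naïve, untreated reference | 1.5 | 1.6% | 6.7% | 12.4% |
| Naïve, untreated reference | 2.0 | 0.2% | 2.3% | 6.2% |
| Naïve, untreated reference | 2.5 | <0.1% | 0.6% | 2.7% |

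For example, m = 0.5 and s = 0.7 give Φ(−0.714) = 0.238. The row with m = 0 needs only symmetry, not normality. Over these ranges the chance is 24% to 50% in adherent switchers and at most about 12% in adherent naïve patients. The gap between the groups remains throughout, but its size depends on the inputs chosen.

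**The case against.** The strongest reply is that this is one interpretive sentence and not a classification rule. The protocol sets no cut-off, no adherent/non-adherent label for individual patients, no reference time for the change and no adherence proportion. Adherence is not an endpoint in Tables 9-1 to 9-3. That stands, and it limits what can be claimed.

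A reader might go further and infer any of the following. The document does not support them.

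- *That the plan misclassifies a definite share of the cohort.* This needs a threshold at zero, a mean change in switchers and a non-naïve share. The protocol states none of them.
- *That safety or growth results will be confounded by adherence.* No analysis by adherence is planned. The subgroups in Section 9.7.2.2 are sex, age, dose, country or region, and Tanner stage. The on-treatment period is defined by dates and not by IGF-I.
- *That using IGF-I SDS both as an endpoint and as an adherence marker is a contradiction.* It makes interpretation harder, but the protocol openly presents the second use as an assumption.

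The second reply is that the problem is already handled. Analyses are repeated by naïve status, and Section 9.3.3 lists duration of previous GH treatment as a covariate. This stands in part: shown by stratum, a near-zero change in switchers would be visible and not buried in a pooled figure. But the repetition is conditional on the data, and within the non-naïve stratum the same assumption still turns no rise into a sign of poor adherence. It also does not separate out naïve children already on somapacitan at consent.

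**Conclusion.** The point holds as a flaw in a stated assumption. An increase in IGF-I SDS can be relied on as a sign of adherence only where the reference value is untreated, and the protocol enrols patients for whom it may not be. This follows from the protocol's own statements and needs no outside figure.

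The reach is narrow: one descriptive secondary reading. The primary ADR endpoint and the neoplasm, T2DM and growth analyses do not depend on it. The size of the error cannot be derived from the document. The range of about 24% to 35% (mean 0.5, SD 0.7 to 1.3) to about half (mean 0) of adherent switchers showing no increase rests on assumed means and SDs, and on reading any change at or below zero as no increase. It is worth correcting before the SAP is finalised because, as written, the sentence gives the wrong reading for adherent switchers.

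**What to change.** In Section 9.7.2.2, qualify the adherence sentence in two steps:

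1. Restrict the increase-based reading to GH-naïve patients who have an IGF-I value from before their first somapacitan dose.
2. For non-naïve patients, and for anyone whose reference value was taken on treatment, describe the IGF-I SDS level by current dose without calling it adherence, and state that adherence cannot be inferred from IGF-I change in them.

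The variables needed are already listed: prior GH exposure and baseline IGF-I in Section 9.3.3, and treatment start date, initial dose and dose changes in Section 9.3.1. The change takes about two sentences and alters neither data collection nor patient management. The price is that adherence is described in fewer patients. How many fewer is unknown, because the protocol states neither the naïve share nor how often a pre-treatment value will be available.
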